### **5.11. The Relationship Between Case Definition 1 and Other Efficacy Endpoints**

In order to establish the interrelationship between the first occurrence of RT-PCR confirmed RSV-mediated LRTD according to case definition 1 and the following endpoints:

- Clinically relevant diseases (phase 3)
- Therapeutic interventions
- Emerging medical resource utilization
- Complication (phase 3)
- Hospitalizations
- And none of the above

The percentage of placebo participants having an RT-PCR confirmed RSV ARI and one of the above endpoints during that ARI will be shown for participants meeting Case Definition 1 versus participants not meeting Case Definition 1, with the corresponding odds ratio and 95% CI.

The analysis will be restricted to placebo participants with any RT-PCR confirmed RSV disease, during the three RSV seasons, from the PPE set.

In case a participant experience two or more RSV ARIs during these three RSV seasons, the same rule will apply similar to a participant experiencing two or more ARIs during the same season (see Section 4.5.1.1).

### **5.12. Connection between Case Definition 1 and patient reported measures, clinical assessment**

In order to establish the interrelationship between the first occurrence of RT-PCR confirmed RSV-mediated LRTD according to case definition 1 and PROs, the following analyses will be performed restricted to placebo participants with any RT-PCR confirmed RSV disease, during the three RSV seasons, from the PPE set.

For the AUC of the change from baseline for the Total RiiQ Respiratory and Systemic symptom score and the RiiQ Lower Respiratory Symptom score, the number of observations, median, first and third quartile, will be calculated for participants meeting case definition 1 and participants not meeting case definition 1, this may also be graphically depicted with boxplots.

In case a participant experience two or more RSV ARIs during the three RSV seasons, the same rule will apply similar to a participant experiencing two or more ARIs during the same season (see Section 4.5.1.1).

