**Table 6: Case Definitions**

Case Definition #1	Case Definition #2	Case Definition #3
≥3 symptoms of LRTI (new onset or worsening)	≥2 symptoms of LRTI (new onset or worsening)	≥2 symptoms of LRTI, OR ≥1 symptom of LRTI combined with ≥1 systemic symptom (new onset or worsening)
RT-PCR confirmation of RSV		

LRTI = lower respiratory tract infection

To meet the primary endpoint criteria for a case definition, the following criteria need to be fulfilled:

a <https://www.cdc.gov/surveillance/nrevss/rsv/region.html>

- The participant must show the necessary number of signs and symptoms (new onset or worsening) according to the considered case definition. Which symptoms will be taken into account and how the number of symptoms will be counted is defined in Section 4.4.2.1.1.
- The considered ARI episode must be RT-PCR confirmed for RSV. RSV RT-PCR confirmation is defined in Section 4.4.2.1.2.

First occurrence of a considered endpoint is defined as the first day of symptoms of the first RSV-confirmed ARI episode where the criteria for the respective case definition are fulfilled on at least one assessment of the considered episode. Only episodes occurring in the first season of the participant are taken into account for the primary analysis.

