**Table 7: Symptoms of Lower Respiratory Tract Infection and Systemic Symptoms as per RiiQ or Clinical Assessment**

	Symptoms from Case Definition	RiiQ Term	Clinical Assessment Term (ARI Days 3-5 Clinical Visit)
Symptoms of LRTI	Cough	Cough	Cough
	Shortness of breath	Short of breath	Dyspnea or decreased oxygen saturation
	Sputum production	Coughing up phlegm (sputum)	Sputum production
	Wheezing	Wheezing	Wheezing or rhonchi, rales or other sign of consolidation
	Tachypnea		Tachypnea
Systemic Symptoms	Fatigue	Fatigue (tiredness)	Malaise (tiredness)
	Fever		Fever
	Feverishness	Feeling feverish or Fever*	

LRTI =lower respiratory tract infection, RiiQ = Respiratory Infection Intensity and Impact Questionnaire

\* Fever defined based on the daily temperature reported from the participants in the eDiary

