**Counting of symptoms during an ARI episode:**

Counting of the number of symptoms with new onset or worsening will be done per day and per assessment (clinical assessment or patient reported outcome in the eDiary or in the eDevice). Therefore, if a subject has several assessments at the same day (e.g. at ARI day 3-5, or by accident two RiiQs at the eDiary during the same day), the case definitions cannot be met by combining symptoms from different assessments, the required number of symptoms must be attained at one assessment.

For example, if at Day 3 a participant reports in the eDiary mild cough and the study staff reports mild wheezing at the same day, this participant does not meet case definition 2, because the 2 LRTI symptoms are reported by 2 different assessments. The participant would meet the case definition only if both symptoms were reported in the eDiary or if both were reported by the study staff in the clinical assessment.

Note: Patient reported outcomes reported in the eDiary and in the eDevice at the same day can be distinguished by the App type ID linked to the device and by the time of reporting.

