#### **4.13. Connection between Primary Endpoint and Patient reported Measures, clinical assessment and frailty index**

In order to establish the interrelationship between the primary endpoints and PROs, the following analyses will be performed restricted to the placebo group. These analyses will be performed on two subgroups of the PPE set:

- participants with any RT-PCR confirmed RSV disease (see [above](#) for definition)
- participants with any ARI (see [Any ARI](#) definition, independently of RSV etiology)

For the following patient reported measures:

- AUC of the change from baseline for the Total RiiQ Respiratory and Systemic symptom score
- AUC of the change from baseline for the Total RiiQ Case Definition symptom score
- AUC of the change from baseline for the Total RiiQ Impact on Daily Activity score
- The change in IADL score between ARI Day 3-5 and baseline
- The change in augmented frailty score between baseline and end of season

The number of observations, median, first and third quartile, will be calculated for participants meeting each case definition and participants not meeting any case definition or not meeting the considered case definition; this will also be graphically depicted with boxplots.

Note: In case a participant experiences two or more ARIs during the study the same rule as for the RiiQ will be used.

As a sensitivity check the same analysis will be performed but without taking into account cough for any of the case definitions.

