## 5.5. PATIENT-REPORTED OUTCOMES

### 5.5.1. Respiratory Infection Intensity and Impact Questionnaire (RiiQ™v2)

For the second and third RSV season, only the total RiiQ Respiratory and Systemic symptom score change from Day 365/Day 730 and the respective AUC will be calculated for RSV ARIs, occurring during the second or third RSV season. For details in calculations see Section 4.5.1.

To align with the phase 3 VAC18193RSV3001 study, also the RiiQ Lower Respiratory Symptom scores (cough, short of breath, coughing up phlegm (sputum) and wheezing) and the respective AUC will be calculated for RSV ARIs during the second and third RSV season. Post-hoc analysis will be done for the first RSV Season.

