## 5.8. Clinically Relevant Diseases

Clinical relevant diseases associated with RSV ARIs as defined in the phase 3 VAC18193RSV3001 study will be analyzed:

- Hospitalization
- Emergency department visit (as assessed on the eCRF medical encounters form and MRU pages [emerging MRU to be summarized])
- At least one of the following complications: asthma, COPD, respiratory distress, bronchitis, bronchial hyperreactivity, CHF, cardiac arrhythmia, renal impairment or the presence of X-ray or radiological confirmed pneumonia, respiratory arrest and/or failure, pulmonary embolism, pleural effusion, atelectasis, acute coronary events, acute cerebrovascular events, altered mental status, seizure, syncope, systemic inflammatory response syndrome (SIRS), new neurological deficit, asthenia, dehydration or metabolic disturbances.  
See [Attachment 10](#) for the complication terms. These terms will be reported in the AE domain.  
Asthma and chronic obstructive pulmonary disease (COPD) exacerbation supporting LRTD reported in the medically attended ARI form will also be counted, as well as X-ray or radiological confirmed pneumonia from the diagnostic tests form.
- Decreased oxygen saturation defined as oxygen saturation of <92% for participants with a baseline oxygen saturation of  $\geq 92\%$  at randomization; for participants with baseline oxygen saturation <92%, decreased oxygen saturation is defined as a  $\geq 3\%$  decrease in their oxygen saturation from baseline
- Tachypnea (at least Grade 2, see Section 4.8)
- Need of supplemental oxygen
- Hypotension (at least Grade 3, see Section 4.8)
- Pulmonary function test results supporting diagnosis of LRTD
- Arterial blood gas results supporting diagnosis of LRTD

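### Section 5.12 relates Case Definition 1 to patient-reported burden using only scores that contain its own symptom items; Section 5.11 shares the problem in two of its endpoints

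*SAP*

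**What the plan says.** Section 5.12 takes placebo participants in the PPE set with any RT-PCR-confirmed RSV disease over the three seasons, splits them by whether they met CD1, and reports N, median and quartiles (boxplots optional) "For the AUC of the change from baseline for the Total RiiQ Respiratory and Systemic symptom score and the RiiQ Lower Respiratory Symptom score". Its stated aim is to establish how CD1 and PROs are related.

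Table 6 defines CD1 by "≥3 symptoms of LRTI (new onset or worsening"), with RSV confirmed by RT-PCR. Section 4.4.2.1.1 adds that "the required number of symptoms must be attained at one assessment", which may be the RiiQ on either device or the clinical assessment. In Table 7 the RiiQ items that count are cough, short of breath, phlegm and wheezing. Section 5.5.1 defines the "RiiQ Lower Respiratory Symptom scores (cough, short of breath, coughing up phlegm (sputum) and wheezing").

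Section 5.11 gives odds ratios with 95% CIs, in the same placebo population, for CD1 met versus not met. Its endpoints are "Clinically relevant diseases (phase 3"), therapeutic interventions, emerging medical resource use, complications (phase 3), hospitalizations, and none of these. The phase 3 clinically relevant disease list in Section 5.8 includes "Tachypnea (at least Grade 2, see Section 4.8") and decreased oxygen saturation.

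**The concern.** A classifier and the measure used to judge it should not be the same thing. In 5.12 participants are sorted by whether enough of four RiiQ items rose above baseline, and the groups are then compared on how far those same items rose above the same baseline in the same episode. A higher AUC in the CD1 group would be expected even if CD1 told us nothing about any other aspect of illness.

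This matters because Section 1.6 makes CD1 the only LRTD case definition analysed for seasons two and three and across seasons. Section 5.12 is where the plan relates CD1 to what patients report. As written it cannot show that CD1 marks illness patients feel beyond the symptoms that define it.

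**Working it through.** The SAP gives no sample size, effect or expected figure for 5.11 or 5.12, so there is nothing of its own to reproduce.

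**1. Item overlap in 5.12**

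| Measure | Source | Items | Shared with CD1's RiiQ items |
|---|---|---|---|
| RiiQ Lower Respiratory Symptom score | 5.5.1 | 4 | 4/4 = 100% |
| Total RiiQ Respiratory and Systemic score | 4.5.1 | 6 respiratory + 7 systemic = 13 | 4/13 = 31% |

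Tachypnea counts towards CD1 only through the clinical assessment.

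**2. The mechanical rise.** On a RiiQ assessment that meets CD1, at least three of the four items are at least one grade above baseline. If no other item has fallen below baseline, and the Lower Respiratory score is a mean like the other RiiQ totals, it has risen by at least 3/4 = 0.75 and the Total score by at least 3/13 = 0.23. A participant who never meets CD1 on the RiiQ has at most two of the four items raised at any assessment. Two items going from none to severe would still give 2 × 3/4 = 1.5, so the ordering is not a logical certainty and the size of the difference carries information.

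**3. How often the direction appears with no real relationship.** All 13 symptoms were simulated as mutually independent, so any link can come only from shared items. Assumptions, not from the SAP: item prevalence 0.3, 0.5 or 0.7; severity 1–3 with equal probability; 10 days; a present item reported on 80% of days; 20, 40 or 80 placebo RSV cases; CD1 met on the RiiQ; up to 1000 studies per setting, keeping those with at least two participants in each group.

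| AUC of | Median ratio, CD1 met / not met | Studies with higher median in CD1 group |
|---|---|---|
| Lower Respiratory (4 items) | 1.92–3.18 | about 100% |
| Total (13 items) | 1.19–1.59 | 92–100% |
| The nine non-LRTI items | 0.99–1.01 | 48–52% |

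If CD1 can also be met on a clinical assessment independent of the RiiQ, the first two ratios fall to 1.57–1.71 and 1.14–1.22 but stay above 1. Other assumptions (14 diary days, 30–100 cases) gave 95–100%, 83–99% and 48–54% for the last column.

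**4. What 5.12 leaves out.** The season 1 counterpart, Section 4.13, includes overlapping measures such as the "AUC of the change from baseline for the Total RiiQ Case Definition symptom score", but also the Daily Activity AUC and the IADL change, which share no CD1 item, and a repeat without cough. Section 5.12 carries over none of these. Its title names clinical assessment, yet no such measure is listed.

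**5. Overlap in 5.11**

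- Respiratory rate: CD1 counts more than 20 breaths per minute when baseline is 20 or below, or missing. Grade 2 in Table 11 starts at 21, which is the same cut.
- Oxygen saturation: CD1 uses below 90%; Section 5.8 uses below 92%. With baseline at or above 92%, every CD1 desaturation is also an outcome event. With baseline below 90%, both rules are a fall of at least 3%.
- Complications: the Attachment 10 terms include wheezing, productive cough, rales, rhonchi, dyspnoea and tachypnoea. Complications are an endpoint in their own right and also a component of clinically relevant disease.
- Therapeutic interventions, medical resource use and hospitalizations use no CD1 symptom item.

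With independent signs (assumed prevalence: cough 0.8, sputum 0.5, wheezing 0.3, dyspnea 0.3, tachypnea 0.05–0.20, SpO2 below 92% 0.02–0.05, all other clinically relevant disease 0.05–0.30), the null odds ratio for clinically relevant disease was 1.40–4.26. With tachypnea and oxygen saturation removed from the outcome it was 0.98–1.00. A second set of assumptions (tachypnea 10–30%, SpO2 falls 5–10%, 60–150 cases) gave a median of 1.3–1.6, with the 95% CI excluding 1 in 4–25% of trials against 3–5% without the shared signs. The complication terms were not simulated.

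**The case against.** The best defence is that 5.12 is descriptive. It has no test, confidence interval or threshold, and no decision depends on it. CD1 can be met by mild symptoms at one assessment, while the AUC integrates severity over the episode, so how much worse and longer CD1 illness runs is a real finding. Nine of the 13 Total items lie outside CD1, so that measure is diluted rather than circular. PGI AUCs are already planned by vaccine group in 5.5.2.1. All of this stands and limits the weight of the point. It does not supply a comparison by CD1 status on any patient-reported measure outside the definition, which is what the stated aim needs.

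A reader might infer that 5.11 is equally circular, or that the three-season analysis has no external criterion at all. The documents do not support either reading. Section 5.11 sets CD1 against hospitalizations, medical resource use and therapeutic interventions in the same population, and none of these is built from CD1 items. Even for clinically relevant disease the overlap concerns some components of a nine-part list, and neither tachypnea nor desaturation alone makes a CD1 case. The null results in the working are far from guaranteeing an association.

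A reader might also want 4.13 and 4.9.2 changed. Section 4.13 already has non-overlapping measures and both sections repeat the analysis without cough, so relabelling there would be preference rather than correction.

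**Conclusion.** The point holds for 5.12. Both of its measures contain CD1's RiiQ items, one wholly and one in 4 of 13 items. The direction of the difference is near certain for the Lower Respiratory AUC and strongly favoured, though diluted, for the Total AUC. Only the size is informative, and no patient-reported measure outside the definition is compared. The aim of establishing a relationship with PROs is not met as written.

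For 5.11 it holds only for phase 3 clinically relevant disease and complications; the none-of-the-above row inherits it as their complement. The other three endpoints are sound external criteria.

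The item counts and cut-offs come straight from the SAP. The simulated figures rest on assumed frequencies and case numbers; they show the mechanism and do not forecast this trial. The analyses are exploratory and restricted to placebo, and no vaccine efficacy estimate or success criterion is affected. It is worth correcting because the correction is cheap.

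**What to change.** In 5.12, add the comparison by CD1 status on the AUC of PGI-S, the AUC of the change in PGI-H, and days to return to usual health. Sections 4.5.2, 4.17, 5.5.2 and 5.5.2.1 already derive these for RSV ARIs in all three seasons. The Daily Activity AUC is not the natural choice, because 5.5.1 limits seasons two and three to two RiiQ symptom scores. Present the Lower Respiratory Symptom AUC as a description of cases only.

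Two details need a line each. PGI-H runs in opposite directions in 4.5.2 and 5.5.2, so the pooled analysis should state that the 5.5.2 scoring applies to season 1 as well. And if the PGI AUCs stop at ARI resolution, as the RiiQ AUCs do, their window still depends on respiratory symptoms (4.4.2.1.3), so days to return to usual health should be read alongside them.

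In 5.11, repeat two odds ratios: clinically relevant disease without tachypnea, decreased oxygen saturation and the complication terms that restate CD1 symptoms, and complications without those terms.

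The cost is SAP wording and a few table rows, with no new data. The reported association will probably look weaker.

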### **5.13. Viral Load**

Viral loads will be analyzed similar to season one (see Section 4.14) for participants with any RT-PCR-confirmed RSV disease and for participants fulfilling Case Definition 1, during the second or third RSV season and across the three RSV seasons.

The viral load analysis will be conducted separately for RSV A and RSV B infected participants. The overall RSV viral loads will not be calculated.

#### **5.14. Approximate ARI surveillance compliance**

The responsiveness of the participants to the ARI surveillance question will be summarized for both groups, for the second and third RSV season, similar to the first RSV season. A summary might be added across the three RSV seasons. For details, refer to Section 4.15. For the second RSV season, however, the number of weeks between the Day 365 visit and the end of the ARI surveillance (Day 730a) or day of discontinuation (in case of early discontinuation) will be used in step 1. A similar calculation will be done for the third RSV season based on the Day 730 visit and the end of the ARI surveillance (15th April 2022). Note: in case an ARI episode extends over multiple seasons, the respective duration in the considered season is taken into account for the calculations. Note that as ARI surveillance during the 1st season was stopped at 20 March 2020, for ARIs during the 1st Season, only the duration up to 20 March should be taken into account for the calculation of the approximate ARI surveillance.

#### **5.15. ARI MISSING DATA**

The same analysis as in the first RSV season will be conducted, for the second and third RSV season for ARI missing data. See Section 4.16.

---

a For participants without a Day 730 visit, the second RSV season will be cut off at the relative Day 730 (given that they did not discontinue before) to calculate the number of weeks in step 1. Additionally, ARIs starting in the second RSV season lasting longer than this relative Day 730 will also be cut off at the relative Day 730 in step 2. Finally, when calculating the number of surveillance questions answered, the ones after this relative Day 730 visit will not be counted.

---

## ATTACHMENTS

### Attachment 1: Transforming Solicited AEs into Analysis Format

Solicited AEs are recorded by event and relatedness on the CE domain, similar to the format of unsolicited AEs. The reported start date of the AE on the CE domain equals the date of first occurrence of the solicited AE. The last reported date is used as the end date of the AE, regardless of possible changes in grade or time gaps also taking into account if the AE continues after Day 8. The investigators' opinion about the maximum grade over the duration of the AE will be reported. All solicited events are included on the CE domain, even when no such event occurred. In that case, the maximum grade is missing on the CE domain. These records with missing grade will not be used to construct the analysis dataset for solicited AEs. Note: Mapping of CE data to the solicited AE ADaM will occur in a similar way as unsolicited AEs are mapped in the unsolicited AE analysis database. It is possible that the investigators' assessment as captured in CE differs in grade with the diary data (recorded by day on the FA and VS domain). It is the CE data that will be used when creating ADaMs, tables and listings.

#### Notes:

For solicited AEs time should not be taken into account to allocate an event to a phase, the event is per definition of solicited AEs collected post-dose and should therefore not be allocated to inactive phases.

Duration will be based on the end date – onset date + 1. This duration may differ from the duration in the AE/CE domain because of some remapping before the Season 2 analysis. From that point onwards, the maximum duration for solicited AEs on the CE domain is 8 days. If the AE continues after Day 8, a record will be added to the AE domain, with the same start and end date as the AE had on the CE domain. The duration in the AE domain will differ however, as it will only start counting from Day 8 onwards.

The time to first onset is defined as (date of first onset – reference date + 1). The reference date is the start date of the vaccination period.

[figure not shown]
## Attachment 2: Real World Evidence

Real World Evidence (RWE) will be used to calculate the information fraction at potential interim analyses. The required RWE consists of:

- historic RSV case data over a time for number of past RSV season and
- continuous reporting of RSV caseloads over the ongoing season in the study region.

Example of these data can be found for Western Australia at [https://ww2.health.wa.gov.au/Articles/F\\_I/Infectious-disease-data/Virus-Watch](https://ww2.health.wa.gov.au/Articles/F_I/Infectious-disease-data/Virus-Watch) (Virus Watch "Current Edition" and "Past Editions") and for New South Wales (Australia) at <https://www.health.nsw.gov.au/Infectious/Influenza/Pages/reports.aspx> ("Past influenza surveillance reports" and "Monthly surveillance reports"). From previous years, the general distribution of the RSV case load over the season will be described and modeled. The data from the case load for the current RSV season will then be used to estimate the percentage of RSV cases over the complete year that already have been observed by the time of the IA,  $P_{IA}$  – see below for a graphical presentation. An effort will be made to identify the relevant RWE data for all study regions. If no data is available for the all study regions, extrapolations may be made from neighboring regions.

